5.1 Study Visits

All procedures and assessments are conducted for research purposes.

5.1.1 Visit 1 (Screening)

Subjects will be asked to sign a consent form. An oral exam will be conducted to ensure good oral hygiene. A blood or urine sample will be collected for pregnancy testing, if applicable. A blood sample will be collected to assess liver function (CMP) and clotting function (PT and INR). A mucositis assessment (CTAE version 4.0 and WHO Oral Toxicity Scale) will be conducted and documented by a health provider (Appendix B). This visit will take approximately one hour.

5.1.2 Visit 2

5.1.3 THIS VISIT MUST OCCUR WITHIN 48 HOURS AFTER THE SCREENING VISIT. IF VISIT 2 OCCURS ON A DIFFERENT DAY THAN VISIT 1, ANOTHER MUCOSITIS ASSESSMENT (CTAE VERSION 4.0 AND WHO ORAL TOXICITY SCALE) WILL BE CONDUCTED AND DOCUMENTED BY A HEALTH PROVIDER (APPENDIX B) AND WILL BE CONSIDERED THE BASELINE ASSESSMENT. THE PROVIDER WILL ALSO ASK THE SUBJECT TO COMPLETE A SUBJECT SELF-ASSESSMENT (APPENDIX C). SUFFICIENT MOUTH RINSE WILL BE GIVEN TO THE SUBJECT FOR THE FIRST WEEK OF THE STUDY. THE DAILY LOG (APPENDIX A) AND THE PATIENT SELF-ASSESSMENT TOOL (APPENDIX C) WILL BE GIVEN TO THE SUBJECT. THE SUBJECT WILL BE ASKED TO COMPLETE THE LOG EVERY DAY UNTIL VISIT 3. THE SUBJECT WILL BE ASKED TO COMPLETE THE SELF-ASSESSMENT TOOL ON DAY 3 OR 4 AFTER THE FIRST DAY OF TAKING THE MOUTH RINSE. A BLOOD AND SALIVA SAMPLE WILL BE OBTAINED FOR RESEARCH PURPOSES (SECTION 10). THIS VISIT WILL TAKE APPROXIMATELY 30 MINUTES.Phone call 1

On day 3 or 4 after the first day of taking the mouth rinse for the study, the subject will be called by a study staff member, who will review and follow up on any side-effects that the subject is experiencing and answer any questions about the study or study mouth rinse. The staff member will remind the subject to complete a subject self-assessment tool (Appendix C) and the daily log (Appendix A) and bring them to the next visit. The phone call will take about 15 minutes.

5.1.4 Visit 3

This visit will occur 7 days (+/- 1 day) after Visit 2. A mucositis assessment (CTAE version 4.0 and WHO Oral Toxicity Scale) will be conducted and documented by a health provider (Appendix B), who will also review and follow up on any side-effects that the subject is experiencing and check the daily log (Appendix A) to ensure that the subject is complying with the study. Sufficient mouth rinse will be given to the subject for the second week of the study. A blood sample will be obtained to assess liver function (CMP) and clotting function (PT and INR). A blood and saliva sample will be obtained for research purposes (section 10). This visit will take approximately 30 minutes.

5.1.5 Phone call 2

On day 10 or 11 after the first day of taking the mouth rinse for the study, the subject will be called by a study staff member, who will review and follow up on any side-effects that the subject is experiencing and answer any questions about the study or study mouth rinse. The staff member will remind the subject to complete a subject self-assessment tool (Appendix C) and the daily log (Appendix A) and bring them to the next visit. The phone call will take about 15 minutes.

5.1.6 Visit 4

This visit will occur 7 days (+/- 1 day) after Visit 3. A mucositis assessment (CTAE version 4.0 and WHO Oral Toxicity Scale) will be conducted and documented by a health provider (Appendix B), who will review and follow up on any side-effects that the subject is experiencing and obtain the daily log (Appendix A) from the subject. A blood sample will be obtained to assess liver function (CMP) and clotting function (PT and INR). A blood and saliva sample will be obtained for research purposes (section 10). If the mucositis score \leq Grade 2 but is unresolved, then the subject will continue to receive the study mouth rinse (curcumin or standard mouth rinse) until the mucositis is resolved (Grade 0). Sufficient mouth rinse will be given to the subject for the subsequent week of the study. This visit will take approximately 30 minutes.

5.1.7 Phone call 3

On day 17 or 18 after the first day of taking the mouth rinse for the study, the subject will be called by a study staff member, who will review and follow up on any side-effects that the subject is experiencing and answer any questions about the study or study mouth rinse. The staff member will remind the subject to complete a subject self-assessment tool (Appendix C) and the daily log (Appendix A) (only if they are still on study mouth rinse) and bring them to the next visit. The phone call will take about 15 minutes.

5.1.8 Visit 5

This visit will occur 7 days (+/- 1 day) after Visit 4. A mucositis assessment (CTAE version 4.0 and WHO Oral Toxicity Scale) will be conducted and documented by a health provider (Appendix B), who will review and follow up on any side-effects that the subject is experiencing and obtain the daily log (Appendix A) from the subject (if the subject is still on study mouth rinse). A blood sample will be obtained to assess liver function (CMP) and clotting function (PT and INR). A blood and saliva sample will be obtained for research purposes (section 10). If the mucositis score \leq Grade 2 but is unresolved, then the subject will continue to receive the study treatment (curcumin or standard mouth rinse) until the mucositis is resolved (Grade 0). Sufficient mouth rinse will be given to the subject for the subsequent week of the study. This visit will take approximately 30 minutes.

5.1.9 Weekly phone calls to subjects receiving study mouth rinse (curcumin or standard mouth rinse)

Between each visit, each subject will be called by a study staff member, who will review and follow up on any side-effects that the subject is experiencing and answer any questions about the study or study mouth rinse. The staff member will remind the subject to complete a subject self-assessment tool (Appendix C) and the daily log (Appendix A) and bring them to the next visit. The phone call will take about 15 minutes.

5.1.10 Weekly visits for subjects receiving study mouth rinse (curcumin or standard mouth rinse)

A mucositis assessment (CTAE version 4.0 and WHO Oral Toxicity Scale) will be conducted and documented by a health provider (Appendix B), who will review and follow up on any side-effects that the subject is experiencing and obtain the daily log (Appendix A) from the subject. A blood sample will be obtained to assess liver function (CMP) and clotting function (PT and INR). A blood and saliva sample will be obtained for research purposes (section 10). If the mucositis score \leq Grade 2 but is unresolved, then the subject will continue to receive the study mouth rinse (curcumin or standard mouth rinse) until the mucositis is resolved (Grade 0). Sufficient mouth rinse will be given to the subject for the subsequent week of the study. This visit will take approximately 30 minutes.

5.2 Study Calendar

Study Procedure	Visit 1 (Screening)	Week 1		Week 2		Week 3		Week 4- mucositis resolution		Final visit
	day -1	Visit 2: day 0	Phone call 1: day 3	Visit 3: day 7	Phone call 2: day 10	Visit 4: day 14	Phone call 3: day 17	Visit: For phase II: weekly cycle repeated until mucositis is resolved (and no AEs)	Phone calls	
activity window		At or w/in 48hr of Visit 1	+ 1 day	+/- 1 day	+ 1 day	+/- 1 day	+ 1 day	+/- 1 day	+ 1 day	+/- 1 day
Sign Informed Consent	X									
Oral exam for hygiene	X									
Pregnancy test	X ¹									
Provider mucositis assessment ²	X	X ³		X		X		X ^a		X
Provider supplies study mouth rinse		X		X		X ^a		X ^a		X
Provider supplies study journal, self-assessment		X		X		X ^a		X ^a		X
Provider collects journal and self-assessments				X		X		X ^a		X
Remind subject to complete self-assessment		X	X		X		X		X ^a	
Blood collection for liver function (CMP) ⁴	X			X		X		X ^a		X
Blood collection for clotting (PT and INR) ⁴	X			X		X		X ^a		X
Research blood collection ⁵		X		X		X		X ^a		
Research saliva collection ⁵		X		X		X		X ^a		
Collect AEs			X	X	X	X	X	X ^a	X ^a	X
Review of concomitant medications	X	X		X		X		X ^a		X

¹ Blood or urine pregnancy test, if not already done as part of standard of care

² Includes CTAE version 4.0 and WHO oral Toxicity scale.

³ Mucositis assessment at Visit 2, only if a different day than Visit 1 (does not need to be repeated if Visit 1 and 2 are done on the same day)

⁴ Does not need to be repeated if already done for standard of care.

⁵ 6 ml of peripheral blood into a non-anti-coagulated tube, 2 ml saliva into a sterile tube; processed and stored as described in the operations manual.

^a Only if subject is still taking study mouth rinse based on improvement of mucositis at each visit, beginning at visit 4.

5.3 Preparation of Standard Mouth Rinse

The standard mouth rinse will be prepared by the pharmacy and provided in 200 mL bottles and will utilize measured dosing cup for accurate dosing. The standard mouth rinse contains 40% Benadryl, 40% Maalox, and 20% of 2% Viscous Lidocaine. Subjects will use 15 ml each of the 3 times they rinse their mouths each day.

5.4 Preparation of Study Mouth Rinse (Curcumin)

The appropriate daily dose of study drug (powder) will be dispensed by the pharmacy in a plastic amber vial. Subjects will receive 8 vials (1 week supply +1 in case of spilled/lost dose) of curcumin powder and vials of sterile water to prepare their study mouth rinse at home. The volume of water dispensed in each vial will vary based on the dose of curcumin the subject is assigned to. Regardless of dose, all prepared curcumin solutions will total 45 ml in volume. These vials will be stored at room temperature. Subjects will be instructed to add a vial of sterile water to each vial of curcumin powder on each day. Subjects will shake the vial to disperse the curcumin powder and then use a third of the volume (15 mLs) three times a day. Subjects will be provided a plastic dosing cup to help measure out 15 mLs. Subjects will store the curcumin suspended in water at room temperature until it is used up. Subjects will obtain a second one week supply of study mouth rinse, prior to preparation of day 7 (+/- 1 day) dosing in order to ensure no break in treatment.

5.5 Study Drug (Curcumin) Dose

The recommended oral dose of curcumin is 1-3 gram/day for healthy adults. Previous studies in adults with gastrointestinal disorders ranged from 72 mg/day to 2 g/day and the dose duration lasted from 1 to 6 months (IND Table 2). The dosing regimen for topical use of curcumin in a recent study in adolescents and young adults with oral mucositis[14] was 165 mg twice per day for 2 weeks (330 mg/day).

To determine MTD in this study, the first dose level will be the dose used in the aforementioned study[14], multiplied by 3 (adult dose is 3 times the pediatric dose), which is 1 gram/day. The subsequent dose levels will be 3 grams/day, 6 grams/day and 9 grams/day. The duration of patient exposure to the drug will be 3 times a day for 30 seconds of topical exposure each time before swallowing, for 14 days.

5.6 Determination of MTD

The MTD will be determined as follows: If a DLT occurs in any one of the 3 patients at a specific dose level, an additional 3 patients must be treated at that dose level to achieve statistical validity of the MTD. If 2 of the 6 patients (17%) at a dose level develop a DLT, the previous dose level will be used as the MTD. If no DLT is observed, then the MTD will be the highest dose. To ensure safety of subjects at each dose level, all assessments will be completed at Visit 5 for subjects at a dose level before another subject is given study drug at the

subsequent dose level.

6. Expected Adverse Events

Toxicities will be graded by health care providers using the Common Terminology Criteria for Adverse Events (CTCAE) Version 4.0 weekly after initiation of study mouth rinse until mucositis is resolved (Grade 0) (see Provider Assessment in calendar, section 5.2). Toxicities will be assessed by subject self-evaluation during study mouth rinse administration between clinic visits (see Subject Assessment in calendar, section 5.2).

Very few studies have reported any severe or serious side effects from curcumin and most studies have involved oral administration of curcumin. No major toxicity has been found in studies where curcumin is used short-term. Increased bleeding may occur due to inhibition of platelet aggregation (very rare). Possible other side effects associated with curcumin include: vomiting, nausea, rash and GI distress. In a study of subjects with colon cancer, oral curcumin at doses ranging from 0.45 to 3.6 gram/day for 1 to 4 months was associated with nausea and diarrhea and caused an increase in serum alkaline phosphatase and lactate dehydrogenase[15]. In one study of patients with advanced pancreatic cancer, 5 of the 17 patients receiving oral curcumin (8 gram/day) in combination with gemcitabine reported intractable abdominal pain after a few days to 2 weeks of curcumin intake[16]. In a recent study of topical curcumin for mucositis in juveniles and children[14], there were no oral adverse events documented and no systemic adverse events that possibly could be related to the use of the curcumin mouthwash.

Patients will receive full supportive care as appropriate. The rationale for treatment, dosage and the date of treatment will be recorded in the medical record.

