6.2 Criteria for Subject Removal

A subject will be removed from the study for the following reasons:

- Dose limiting toxicity.
- No improvement in mucositis after 14 days of taking the study mouth rinse.
- Patient decision to withdraw consent or discontinue the study.
- Deemed by the physician to be the best medical interest of the patient.
- At the discretion of the investigator, patients who are non-compliant.

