6.3 Criteria for Study Discontinuation

If 2 patients develop a DLT at dose 1, then the trial will be closed due to unacceptable toxicity. If any patient has Grade V toxicity, then, the trial will be placed on immediate hold until the protocol investigators, the sponsor of the IND, the IRB and the FDA have been notified and a determination has been made as to the re-opening of this trial.

If < 5 of the first 10 subjects in the curcumin arm of the second part of the study have Grade 0 mucositis (CTAE version 4.0 and WHO Oral Toxicity Scale) at Visit 4, then the study will be discontinued due to lack of activity.

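### At doses 2 to 4, section 5.6 gives no stopping rule when 2 or 3 of the first 3 patients have a DLT

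*Combined protocol and SAP*

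**What the plan says.** Section 5.6 of the combined protocol and SAP provides for three outcomes at a dose level:

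- A DLT among the first three: "If a DLT occurs in any one of the 3 patients at a specific dose level, an additional 3 patients must be treated" at that level.
- Two DLTs after expansion: "If 2 of the 6 patients (17%) at a dose level develop a DLT, the previous dose level will be used as the MTD".
- No DLT: the highest dose becomes the MTD.

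Section 3 sends the reader to section 2 for the definition of the MTD, but section 2 lists only objectives, so 5.6 stands alone.

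Several other provisions bear on a toxic dose level:

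- Section 6.1 defines a DLT as any toxicity of grade 3 or higher, or an allergic response of grade 2 or higher.
- Section 6.2 removes the individual subject, either for a DLT or when "Deemed by the physician to be the best medical interest of the patient".
- Section 6.3 has one count-based stop: "If 2 patients develop a DLT at dose 1, then the trial will be closed due to unacceptable toxicity". It also has a hold for deaths: "If any patient has Grade V toxicity, then, the trial will be placed on immediate hold".
- Section 5.6 delays escalation: "all assessments will be completed at Visit 5 for subjects at a dose level before another subject is given study drug at the" next level.
- Section 12 provides for weekly toxicity review by the Principal Investigator and for IRB review of trends.

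**The concern.** With three patients at a level there are four possible DLT counts: 0, 1, 2 and 3. Section 5.6 clearly handles 0 and 1. What it requires for 2 or 3 depends on how its first sentence is read.

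- **At least one DLT.** Three more patients have to be treated, although the level already has two or three DLTs. If the 2-of-6 limit means 2 or more, the dose is already rejected. The extra patients carry risk and cannot change the MTD.
- **Exactly one DLT.** No action is given, and no MTD decision follows, because the only rejection rule is written for six patients. The team would have to choose between stopping, expanding and stepping down, and the dose taken into the 46-patient randomized part would not be set by the protocol.

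The sponsor did write a two-DLT stop for the lowest dose (1 g/day). It is missing for 3, 6 and 9 g/day, where toxicity is more to be expected.

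**Working it through.** **1. The plan's own figure.** Section 5.6 attaches 17% to 2 of 6. This does not reproduce: 2/6 = 33.3%, while 1/6 = 16.7%. The intended limit is therefore not certain. A limit of 1 in 6 would make the expansion pointless, since every expanded level already has one DLT, so 2 of 6 is the likelier intent. The gap does not depend on the answer: 2/3 = 66.7% exceeds both.

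**2. Does any other section fill the gap at doses 2 to 4?**

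| Provision | What it controls | DLT-count stop at doses 2 to 4? |
|---|---|---|
| 6.3, two DLTs | Dose 1 only | No |
| 6.3, Grade V hold | Deaths, at any dose | No; DLTs start at grade 3 (grade 2 if allergic) |
| 6.2, removal | The affected subject | No |
| 5.6, Visit 5 hold | Start of the next level | No; enrolment at the same level is not limited |
| 12, review | Principal Investigator and IRB judgement | No count trigger |

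**3. How often the uncovered outcome would arise.** The inputs are a cohort of 3 (section 3) and a true DLT rate p. The documents give no such rate, so p is assumed from 10% to 50%.

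- Chance of 2 or more DLTs in the first 3: P = 3p²(1 − p) + p³. At p = 0.30 this is 3 × 0.09 × 0.70 + 0.027 = 0.216.
- Expected extra patients per opened level, if three more are then treated: 3P.
- Expected extra DLTs per opened level: 3p × P.

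| Assumed p | P | Extra patients | Extra DLTs |
|---|---|---|---|
| 10% | 0.028 | 0.084 | 0.008 |
| 20% | 0.104 | 0.312 | 0.062 |
| 30% | 0.216 | 0.648 | 0.194 |
| 40% | 0.352 | 1.056 | 0.422 |
| 50% | 0.500 | 1.500 | 0.750 |

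These are averages over all opened levels. Once the outcome has occurred, all three extra patients are exposed, with 3p further DLTs expected (0.9 at p = 0.30).

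**4. A rough anchor near the top dose.** Section 6 reports that "5 of the 17 patients receiving oral curcumin (8 gram/day) in combination with gemcitabine reported intractable abdominal pain". This is 5/17 = 29.4%. The events are ungraded and come from another population on combination treatment, so this is not a DLT rate. Taken only as a reference value, it gives P = 0.209, 0.626 extra patients and 0.184 extra DLTs. Over its exact (Clopper-Pearson) 95% interval, 0.103 to 0.560, P runs from 0.030 to 0.589, extra patients from 0.089 to 1.767, and extra DLTs from 0.009 to 0.989.

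**The case against.** The strongest reply is that the intent can be inferred. Both 5.6 and 6.3 treat two DLTs as the limit, and two DLTs in three patients already meet a 2-of-6 limit because later patients cannot lower the count. A sensible investigator would stop and use the previous dose, which is the MTD the proposed wording gives. Section 12 also has the Principal Investigator look at toxicity every week and amend the protocol on safety grounds. Sections 3 and 8 budget only one expansion in part 1 (12 + 3 = 15 subjects), which bounds planned exposure. Toxicity may also be low: section 6 says "No major toxicity has been found in studies where curcumin is used short-term".

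Much of this stands as mitigation:

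- The two harms are alternatives. The extra-patient figures apply under the at-least-one reading, or if the team chooses to expand; the undefined MTD applies under the exactly-one reading.
- Because of the single budgeted expansion, the per-level figures should not be added across doses 2 to 4.
- The 5-of-17 figure is weak, and its sampling interval does not capture the main uncertainty, which is whether it is relevant at all.
- At a 10% DLT rate the problem is rare.

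It does not close the gap. The inference is reasonable but unwritten, and it runs against a sentence that makes treating three more patients mandatory. Sections 3 and 8 also add three subjects when a DLT occurs, with no exception for two or three DLTs. The enrolment budget is not a safety stop, and review by judgement is not a DLT-count rule.

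**Conclusion.** The concern holds. For 2 or 3 DLTs in the first 3 patients at doses 2 to 4, the protocol either requires further exposure at a dose it will reject or specifies nothing. The chance of meeting this at an opened level is 3% to 50% over assumed DLT rates of 10% to 50%. If three more patients are then treated, the expected excess per opened level is 0.08 to 1.50 patients and 0.01 to 0.75 DLTs. These sizes rest on assumed rates and independent patients; the gap itself rests on the text alone. The statement that extra patients cannot alter the MTD assumes that 2 of 6 means 2 or more. This should be fixed: it affects the rule for the primary objective and patient safety, although clinical oversight partly mitigates it.

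**What to change.** In section 5.6, replace the first two rules with wording to this effect:

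- Expand a level to 6 patients only if exactly 1 of the first 3 has a DLT.
- If 2 or more of the first 3, or 2 or more of up to 6, have a DLT, stop enrolment at that level and use the previous level as the MTD. At dose 1, close the trial under section 6.3.
- State the limit as 2 or more of 6 patients (33% or more), once the sponsor confirms that 2 of 6, and not 1 of 6 (17%), is meant.

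Optionally, state that a second DLT in patient 4 or 5 also stops the level. This spares patients only if dosing in the expansion cohort is staggered.

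The cost is one or two sentences, and no patients are added. Under the at-least-one reading, with 2 of 6 taken as 2 or more, the MTD is unchanged. Under the exactly-one reading, the change supplies a decision that is now missing.

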Careful evaluation to ascertain the toxicity and efficacy of topical curcumin on mucositis will be performed by the Principal Investigator and the research team. For all patients, the Principal Investigator will review all serious adverse events and will monitor the data and toxicities to identify trends weekly during the study. The Principal Investigator will be responsible for revising the protocol as needed to maintain safety. The IRB will review submitted adverse events to also evaluate trends and will require a follow up plan from the Principal Investigator whenever a trend is identified. Independent quality, compliance and safety monitoring of the study will occur at least once each year that the study is enrolling subjects and may include a review of protocol compliance, informed

consent documentation, data collection accuracy, adverse event reporting, patient safety and outcomes analysis.

13. Reporting Requirements

- Subject data accrued on this study will be reported in accordance with 21CFR 312.32.
- This study will utilize the CTCAE Version 4.0 for Adverse Event (AE) Reporting. The CTCAE v4.0 can be downloaded from the CTEP home page (<http://ctep.info.nih.gov>).
- The Principal Investigator will notify the IRB, and the FDA and other regulatory agencies of all serious adverse events as required by law or regulation.
- Reporting requirements to the Aurora IRB is described in IRB SOP RR:403 Ongoing Oversight of Approved Research and Reporting of Problems/Events.
- Reporting requirements to the FDA is described in the “Guidance for Industry and Investigators Safety Reporting Requirements for INDs and BA/BE Studies” December 2012:
<http://www.fda.gov/downloads/Drugs/GuidanceComplianceRegulatoryInformation/Guidances/UCM227351.pdf>.
- All participating investigators will be notified of IND Safety Reports by email.

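### The MTD rule in Section 5.6 labels 2 of 6 patients as 17% (it is 33%) and writes no stop for 2 or 3 DLTs among the first 3 patients at dose levels 2 to 4

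*Combined protocol and SAP*

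**What the plan says.** Part 1 treats 3 patients at each of 4 dose levels (Section 3). Section 5.6 then gives three rules.

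- Expansion: "If a DLT occurs in any one of the 3 patients at a specific dose level, an additional 3 patients must be treated" at that level.
- Step down: "If 2 of the 6 patients (17%) at a dose level develop a DLT, the previous dose level will be used as the MTD".
- No toxicity: "If no DLT is observed, then the MTD will be the highest dose".

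The only other rule based on a DLT count is in Section 6.3, for the lowest dose: "If 2 patients develop a DLT at dose 1, then the trial will be closed due to unacceptable toxicity".

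Sections 3 and 8 size Part 1 as 12 subjects plus 3 more if a DLT occurs. Section 3 adds 46 for Part 2 and gives a total of 61. It also says that the MTD is defined in Section 2, but Section 2 lists only the objectives.

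**The concern.** Finding the MTD is the primary objective, and the MTD is the dose given to the 23 curcumin subjects in Part 2. Section 5.6 is the only place that says how to find it.

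Two things are wrong in that rule. First, its count and its percentage disagree, and they direct different actions when exactly 1 of 6 patients has a DLT. A reader who follows the percentage steps down; a reader who follows the count escalates or, at the top level, keeps that dose. The text does not settle this, because it speaks only of 2 of 6 and of no DLT at all.

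Second, nothing says what happens if 2 or 3 of the first 3 patients at level 2, 3 or 4 have a DLT. If the trigger means at least one DLT, three more patients must be treated at a dose that has already reached the two-DLT count. If it means exactly one, no action is stated.

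There is also a planning mismatch: the stated enrolment pays for one expansion cohort, while the rule allows one at every level.

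**Working it through.** **Printed percentage.** 2/6 = 0.333, or 33%. 1/6 = 0.167, or 17%. The printed figure does not reproduce from the printed count.

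**Which was meant.** A level is expanded only after a DLT. Under a 1-of-6 threshold the level would already have failed at that first DLT, so three more patients could change nothing. Section 6.3 also uses 2 patients. At dose 1, a 1-of-6 threshold would name a previous level that does not exist. All three points favour the count.

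**Enrolment.** 12 + 3 + 46 = 61 reproduces, so one expansion is budgeted. The rule's maximum is 4 levels × 6 = 24 places in Part 1, and 24 + 46 = 70 in total.

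**How often these branches arise.** The documents state no DLT rates, so I assumed five curves over the four levels and enumerated the paths exactly. I took 0 of 3 or 1 of 6 to allow escalation and 2 or more DLTs to end it. For a level with DLT rate p:

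- P(0 of 3) = (1−p)³
- P(exactly 1 of 6, after expansion) = 3p(1−p)² × (1−p)³
- P(2 or 3 of the first 3) = 3p²(1−p) + p³
- P(escalate) = the sum of the first two

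Worked example, p = 0.10 at every level:

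- P(0 of 3) = 0.729.
- P(1 of 6) = 0.243 × 0.729 = 0.177.
- P(escalate) = 0.729 + 0.177 = 0.906.
- P(2 or 3 of the first 3) = 0.028.
- 1 of 6 at the top dose: 0.906³ × 0.177 = 0.132.
- 2 or 3 of the first 3 at levels 2 to 4: 0.028 × (0.906 + 0.906² + 0.906³) = 0.069.
- A level fails with probability 1 − 0.906 = 0.094 under the count, against 1 − 0.729 = 0.271 if 1 of 6 were enough. The gap is the 0.177 at stake in the misprint.

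| Assumed DLT rates, levels 1 to 4 | 1 of 6 at some level | 1 of 6 at top dose | 2 or 3 of first 3, levels 2–4 | More than 15 Part 1 places |
|---|---|---|---|---|
| 5% throughout | 37% | 11% | 2% | 7% |
| 10% throughout | 47% | 13% | 7% | 15% |
| 5/10/15/20% | 47% | 14% | 16% | 17–20% |
| 10/15/20/30% | 45% | 8% | 24% | 18–23% |
| 5/10/20/33% | 43% | 8% | 28% | 17–24% |

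In the last column the lower figure assumes that accrual stops at 2 of the first 3, and the higher one that three more are always treated at levels 2 to 4. All 24 places are needed in under 0.5% of trials on either reading.

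**The case against.** The best defence is that the percentage is a parenthetical misprint with an obvious meaning. The rule works by count, 6.3 repeats the count, and a team used to 3+3 designs would act on it. That largely stands. A reader might infer from the table that 37% to 47% of trials would pick the wrong MTD. The documents do not support that: the figure is the chance that a 1-of-6 result occurs, not the chance that anyone follows the wrong percentage.

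On the missing stop, the defence is that two DLTs already meet the two-patient count, so stepping down is the natural inference, and that the plan has other protections. Under 6.2 ("A subject will be removed from the study for the following reasons") a patient with a DLT comes off study. Under 6.3, "If any patient has Grade V toxicity, then, the trial will be placed on immediate hold". Under Section 12 the Principal Investigator "will monitor the data and toxicities to identify trends weekly during the study" and is responsible for revising the protocol when safety requires it. These soften the gap, but none is a rule that stops a cohort. It would also be too strong to say that the gap distorts dose selection: a level with 2 DLTs has failed whether or not more patients are added.

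A reader might also infer that a previous level with only 3 patients must be expanded to 6 before it is named the MTD, because 5.6 says "an additional 3 patients must be treated at that dose level to achieve statistical validity of the MTD". That phrase applies to a level where a DLT has occurred. For the previous level, 5.6 says without condition that it becomes the MTD. Expanding it would be a design preference and does not correct an error.

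On enrolment, 15 places suffice in most trials under every assumed curve, and Section 3 lets subjects re-enter at a higher dose, so distinct people may be fewer than places. The mismatch is real but minor.

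**Conclusion.** The point holds in a limited form, and two parts need correcting. The 17% is wrong as printed and contradicts the count in the rule for the primary objective; the contradiction matters at 1 of 6, which the text leaves unaddressed. The rule also lacks a written stop for 2 or 3 DLTs among the first 3 at levels 2 to 4. On the at-least-one reading this exposes three further patients at a failed dose, and it leaves the selected dose unchanged.

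The arithmetic (33% against 17%, 24 places against 15, 70 against 61) rests on the documents alone, with the maximum relying on 1 of 6 permitting escalation, which is implied but not written. The frequencies rest entirely on the assumed DLT curves: 2% to 28% for the missing-stop branch, and 7% to 24% for needing more than 15 places. The enrolment figure and the stale cross-reference are minor.

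**What to change.** In Section 5.6:

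- Change 17% to 33% and write the threshold as *at least 2 of up to 6*.
- State that 2 or more DLTs at any level, including among the first 3 patients, stop accrual at that level and make the previous level the MTD, with the trial closed if this happens at dose 1, as in 6.3.
- State that 0 of 3 or 1 of 6 leads to escalation or, at the top dose, makes that dose the MTD.

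In Sections 3 and 8 (minor): give Part 1 as up to 24 dose-level places and the total as up to 70, note that distinct people may be fewer if subjects re-enter, and point the MTD references to 5.6 instead of Section 2.

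The cost is a few sentences and a higher stated maximum that is rarely reached. An explicit stop spares up to three patients treatment at a level that has already failed.
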